3 STUDY DESIGN

This is a Phase Ib/II, multicenter study with a planned enrollment of up to 18 subjects in the Phase Ib portion of the study and 30 subjects in the Phase II portion of the study. The target population for this study is subjects with histologically confirmed diagnosis of CCR5 positive, metastatic triple-negative breast cancer (documented as having HER-2 negative, ER<1%, PR<1% disease) who are naïve to chemotherapy in metastatic setting (first-line) OR have failed first-line combination of chemotherapy and checkpoint inhibitor in metastatic setting (excluding carboplatin). A study flow schematic is presented in [Figure 3-1](#).

Figure 3-1: Study Schematic

Note: 1 treatment cycle = 21 (± 3) days

Note: Scans to be done at the end of 2 cycles (prior to Cycle 3) for the first 12 months and at the end of every 3 cycles (9 weeks) thereafter and at EOT, by CT, PET/CT, or MRI with contrast.

Phase Ib

Phase Ib is a dose escalation phase with 3 dose levels (cohorts) of leronlimab (PRO 140) administered in combination with a fixed dose of carboplatin at AUC 5. This dose finding portion of study will follow a “3+3” designed to determine the maximum tolerated dose (MTD) of leronlimab (PRO 140) administered as subcutaneous injection in subjects with histologically confirmed mTNBC that express CCR5. The MTD is defined as 1 dose level (cohort) below the dose in which dose limiting toxicities (DLTs) were observed in $\geq 33\%$ of the participants.

[figure not shown]
The calculation of the sample size for the Phase Ib trial is based on the traditional 3 + 3 dose escalation scheme which is conducted as follows:

- Subjects are treated in cohorts of three each receiving the same dose. For the assessment of a DLT subjects are observed for 3 weeks (Cycle 1) after the first application of the study treatment.
- If none of the three subjects of a cohort exhibits a DLT, the next cohort of three subjects receives the next higher dose.
- Otherwise, if at least one subject of a cohort exhibits a DLT, a further cohort of three subjects is treated at the same dose level (cohort) without escalating the dose.
- If exactly one out of the six subjects treated at this dose exhibits a DLT, the trial continues as planned at the next higher dose level (cohort).

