- If two or more subjects out of the six subjects treated at this dose exhibit a DLT, the dose escalation stops at that level and the next lower dose is considered as the MTD. When the escalation has stopped, additional subjects will be treated at the MTD to a total of six subjects.

A schematic of the “3 + 3” Dose Escalation Study Design is provided in [Figure 3-2](#).

Cohorts of 3 patients are entered at given dose level K. If no patients have a DLT, then the dose will be escalated to the next dose level, K +1. If more than 1 subject has a DLT then the previous dose level, K -1, will be considered as MTD. If 1 subject has a DLT an additional 3 patients will be treated at this dose level, K. If no further subjects suffer a DLT then the dose level will be escalated to K +1 and if any further subjects have a DLT then the previous dose level, K -1, will be considered the MTD. The MTD will be the maximum dose level with an observed toxicity rate of 0% or 17%.

Figure 3-2: 3+3 Study Design

Note: A standard “3 +3” dose escalation design starting at dose \mathcal{K} . The maximum tolerated dose (MTD) is the highest dose at which 0 or 1 dose-limiting toxicities (DLTs) are observed in six subjects. If de-escalation occurs at the first dose level, the study is discontinued.

Cohort escalation (i.e., the decision to progress from one cohort (dose level) to another) will not proceed until all of the following four events have occurred:

- (1) All study subjects in a given cohort (dose level) have been enrolled, and
- (2) All such subjects have been followed for at least 3 weeks (Cycle 1) after the first injection, and
- (3) The Sponsor’s Medical Monitor has reviewed the available safety data (and has had the opportunity to discuss the data with the CRO’s Medical Monitor and PI, if necessary), and recommends further dose escalation and
- (4) The PI has determined that none of the SAEs or DLTs outlined below has occurred.
 - a. Death in any subject in which the cause of death is judged to be possibly, probably or definitely related to leronlimab (PRO 140)

- b. The occurrence in any subject of an anaphylactic reaction to leronlimab (PRO 140)
- c. The occurrence in any subject of a severe local injection site reaction (Grade 3 which is not resolved or recurs; or Grade 4) that precludes administration of consecutive leronlimab (PRO 140) doses.

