- d. The occurrence in any subject of a life-threatening SAE whose causal relationship to leronlimab (PRO 140) is judged to be probable or definite
- e. The occurrence of one or more non-life-threatening SAEs whose causal relationship to leronlimab (PRO 140) is judged to be definite
- f. The occurrence, in one or more subjects, of Grade 4 laboratory abnormalities, judged to be probably or definitely related to receipt of leronlimab (PRO 140)
- g. The occurrence of hematologic and non-hematological adverse events, judged to be possibly, probably or definitely related to receipt of leronlimab (PRO 140) based on previous clinical experience and that are of CTCAE Grade 3 or greater severity. Permissible exceptions to this rule include Grade 3 fatigue of less than one week duration, and Grade 3 nausea, vomiting, and diarrhea that resolve within 48 hours following institution of appropriate supportive care.
- h. Hy's law
- i. Neutropenic fever
- j. Grade 4+ neutropenia or thrombocytopenia >7 days
- k. Grade 3+ thrombocytopenia with bleeding
- l. Grade 3+ electrolyte abnormality that lasts >72 hours, unless the patient has clinical symptoms, in which case all grade 3+ electrolyte abnormality regardless of duration should count as a DLT. Grade 3+ amylase or lipase elevation NOT associated with symptoms or clinical manifestations of pancreatitis does not need to be counted as a DLT
- m. For patients with hepatic metastases, AST or ALT >8xULN or AST or ALT >5x ULN for ≥ 14 days

If any of the SAEs or DLTs outlined above have occurred, the Data Safety Monitoring Board (DSMB) will conduct an independent review of the data and make a final decision for dose escalation to the next cohort.

The dosing regimen for each cohort is as follows:

- Cohort A: 350 mg leronlimab (PRO 140) SC weekly + AUC 5 Carboplatin every 3 weeks
- Cohort B: 525 mg leronlimab (PRO 140) SC weekly + AUC 5 Carboplatin every 3 weeks
- Cohort C: 700 mg leronlimab (PRO 140) SC weekly + AUC 5 Carboplatin every 3 weeks

Leronlimab (PRO 140) is administered as subcutaneous injection in the abdomen weekly. A total of 350 mg, 525 mg, or 700 mg (175 mg/mL) is delivered as two injections on opposite sides of the abdomen. The 350 mg dose will be delivered as two injections of 1 mL each, 525 mg dose will be delivered as two injections of 1.5 mL each and 700 mg dose will be delivered as two injections of 2 mL each.

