The final decision on the MTD will be made following a review of the study data by the DSMB. Continuation into Phase II of the study will take place after the DSMB meeting.

Once the MTD has been determined, subjects enrolled in lower dose cohorts will be allowed to escalate the dose to the MTD, if acceptable per the Investigator's discretion.

Phase II

Phase II is a single arm study with 30 patients in order to test the hypothesis that the combination of carboplatin AUC 5 intravenously and MTD of leronlimab (PRO 140) SC will increase PFS in patients with CCR5 + mTNBC. PFS in patients with newly recurred TNBC is approximately 5 months.

Leronlimab (PRO 140) will be administered subcutaneously at a weekly MTD dose determined in the Phase Ib portion of the study and carboplatin target of AUC 5 every 3 weeks as combination therapy until disease progression or intolerable toxicity. A de-escalation dose of carboplatin will be allowed based on the toxicity, efficacy evaluation, and clinical judgment by physician.

In both the Phase Ib and Phase II portions of the study, patients will be evaluated for response at the end of 2 cycles (i.e., every 6 weeks) for the first 6 cycles (18 weeks) and at end of 3 cycles (i.e., every 9 weeks) thereafter and at EOT by CT, PET/CT or MRI with contrast (per treating investigator's discretion) using the same method as at baseline. Tumor measurements will be done using RECIST v1.1.

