8.5 INTERIM ANALYSIS

No interim analysis (IA) will be performed for efficacy. There will be a safety review, once all three (or six) subjects from each cohort complete the DLT evaluation period (defined as cycle 1 or the first 21 days of treatment).

The Sponsor's Medical Monitor, CRO Medical Monitor and study investigators must be satisfied with data obtained in Cohort A before allowing subsequent enrollment of Cohort B. Likewise, they must be satisfied with data obtained in Cohort B before allowing subsequent enrollment in Cohort C.

In addition, should any of the following events occur in any cohort during the DLT evaluation period, the Data Safety Monitoring Board (DSMB) will meet to review available study data and make a final decision for dose escalation to the next cohort:

- a. Death in any subject in which the cause of death is judged to be possibly, probably or definitely related to leronlimab (PRO 140)
- b. The occurrence in any subject of an anaphylactic reaction to leronlimab (PRO 140)
- c. The occurrence in any subject of a severe local injection site reaction (Grade 3 which is not resolved or recurs; or Grade 4) that precludes administration of consecutive leronlimab (PRO 140) doses.
- d. The occurrence in any subject of a life-threatening SAE whose causal relationship to leronlimab (PRO 140) is judged to be probable or definite
- e. The occurrence of one or more non-life-threatening SAEs whose causal relationship to leronlimab (PRO 140) is judged to be definite
- f. The occurrence, in one or more subjects, of Grade 4 laboratory abnormalities, judged to be probably or definitely related to receipt of leronlimab (PRO 140)
- g. The occurrence of hematologic and non-hematological adverse events, judged to be possibly, probably or definitely related to receipt of leronlimab (PRO 140) based on previous clinical experience and that are of CTCAE Grade 3 or greater severity. Permissible exceptions to this rule include Grade 3 fatigue of less than one week duration, and Grade 3 nausea, vomiting, and diarrhea that resolve within 48 hours following institution of appropriate supportive care.
- h. Hy's law
- i. Neutropenic fever
- j. Grade 4+ neutropenia or thrombocytopenia >7 days
- k. Grade 3+ thrombocytopenia with bleeding

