2. PROTOCOL DESIGN

2.1 Design Overview

Phase Ib

Phase Ib is a dose escalation phase with 3 dose levels (cohorts) of leronlimab (PRO 140) administered in combination with a fixed dose of carboplatin at AUC 5. This dose finding portion of study will follow a "3+3" designed to determine the maximum tolerated dose (MTD) of leronlimab (PRO 140) administered as subcutaneous injection in subjects with histologically confirmed mTNBC that express CCR5. The MTD is defined as 1 dose level (cohort) below the dose in which dose limiting toxicities (DLTs) were observed in ≥ 33% of the participants.

A schematic of the "3 + 3" Dose Escalation Study Design is provided in Appendix 2.

Cohorts of 3 patients are entered at given dose level K. If no patients have a DLT, then the dose will be escalated to the next dose level, K+1. If more than 1 subject has a DLT then the previous dose level, K-1, will be considered as MTD. If 1 subject has a DLT an additional 3 patients will be treated at this dose level, K. If no further subjects suffer a DLT then the dose level will be escalated to K+1 and if any further subjects have a DLT then the previous dose level, K-1, will be considered the MTD. The MTD will be the maximum dose level with an observed toxicity rate of 0% or 17%. If any of the SAEs or DLTs outlined above have occurred, the Data Safety Monitoring Board (DSMB) will conduct an independent review of the data and make a final decision for dose escalation to the next cohort.

The final decision on the MTD will be made following a review of the study data by the DSMB. Continuation into Phase II of the study will take place after the DSMB meeting.

Once the MTD has been determined, subjects enrolled in lower dose cohorts will be allowed to escalate the dose to the MTD, if acceptable per the Investigator's discretion.

Phase II

Phase II is a single arm study with 30 patients in order to test the hypothesis that the combination of carboplatin AUC 5 intravenously and MTD of leronlimab (PRO 140) SC will increase PFS in patients with CCR5 + mTNBC. PFS in patients with newly recurred TNBC is approximately 5 months.

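### Phase Ib gives two incompatible instructions when two or three of the first three patients have a DLT: expand at the same dose, or stop

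*Protocol*

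**What the plan says.** Protocol Section 3 (Phase Ib) sets out the escalation rule twice, and the Synopsis repeats both versions.

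- **Bullets.** With no DLT in three patients the dose goes up. Otherwise, "if at least one subject of a cohort exhibits a DLT, a further cohort of three subjects is treated at the same dose level". The decision is then taken on six patients: exactly one DLT allows escalation, and "If two or more subjects out of the six subjects treated at this dose exhibit a DLT, the dose escalation stops at that level", with the next lower dose as the MTD.
- **Paragraph after the bullets.** The counts in the first three are treated separately. None: escalate. One: "If 1 subject has a DLT an additional 3 patients will be treated at this dose level, K". More than one: "If more than 1 subject has a DLT then the previous dose level, K -1, will be considered as MTD".

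SAP Section 2.1 carries only the second version: "If more than 1 subject has a DLT then the previous dose level, K-1, will be considered as MTD".

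Several review steps surround the rule. Under Protocol Section 8.5, "There will be a safety review, once all three (or six) subjects from each cohort complete the DLT evaluation period"; SAP Section 4 says the same. If a listed event occurs, the DSMB "will conduct an independent review of the data and make a final decision for dose escalation to the next cohort". Section 12 lets the DSMB recommend stopping the study. On the dose itself, "The final decision on the MTD will be made following a review of the study data by the DSMB".

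**The concern.** The two versions agree at zero and one DLT and part at two or three. The bullets' trigger is a minimum of one, so it takes in 2/3 and 3/3, and their only stopping rule is counted out of six. The paragraph and the SAP stop at that point. A site cannot obey both.

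What is at stake is patient exposure. A site following the bullets would treat three more patients at a dose where at least two of three have already had a DLT, and those patients could not alter the rule-based decision. The first dose level is the plainest case. The note to Figure 3-2 says the study is discontinued if de-escalation is called for there, so the bullets would start three further patients in a study already due to stop.

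**Working it through.** **1. The plan's own figure.** Three dose levels with at most six patients each give 3 × 6 = 18, the stated Phase Ib maximum. It is 18 under either version, including the top-up of the MTD level to six.

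**2. Can the extra patients change the MTD?** After 2/3 or 3/3, three more patients bring the count to between 2/6 and 6/6, that is, at least 33%. This always meets the bullets' stopping rule and the 33% threshold in the MTD definition. It can never be the 0% or 17% that Section 3 allows at the MTD. As a check, all combinations of 0 to 3 DLTs in the first and second three patients at three levels were enumerated: (4 × 4)³ = 4,096 paths. The MTD differs between the two versions in 0 of them. Where enrolment before the top-up differs, it differs by exactly three. This result does not depend on any assumed DLT rate.

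**3. How often would the conflict arise?** The documents give no DLT rate, so true rates p at 350/525/700 mg are assumed.

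- Conflict at a level, once reached: P(at least 2 of 3) = 3p²(1−p) + p³. This is 0.00725 at p = 0.05, 0.028 at 0.10, 0.06075 at 0.15 and 0.104 at 0.20.
- Passing a level: (1−p)³ + 3p(1−p)² × (1−p)³. This is 0.9734 at 0.05, 0.9061 at 0.10 and 0.8138 at 0.15.
- Conflict in the trial: the sum over levels of P(level reached) × P(at least 2 of 3).

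For 10/15/20%: 0.028 + 0.9061 × 0.06075 + 0.9061 × 0.8138 × 0.104 = 0.028 + 0.0550 + 0.0767 = 0.1597.

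Extra patients per trial are 3 × the chance of conflict. Extra DLTs per trial are the sum over levels of the chance of conflict there × 3p. For 10/15/20%: 0.028 × 0.30 + 0.0550 × 0.45 + 0.0767 × 0.60 = 0.079.

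| Assumed DLT rates | Chance of conflict | Extra patients per trial | Extra DLTs per trial | Extra DLTs if conflict occurs |
|---|---|---|---|---|
| 5/5/5% | 2.1% | 0.06 | 0.003 | 0.15 |
| 5/5/10% | 4.1% | 0.12 | 0.010 | 0.25 |
| 10/10/10% | 7.6% | 0.23 | 0.023 | 0.30 |
| 10/15/20% | 16.0% | 0.48 | 0.079 | 0.50 |

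At much higher assumed rates the chance rises: 28.6% at 10/20/33% and 43.8% at 20/33/50%. All these figures assume the written bullets are followed with no discretionary halt, so at each set of rates they are upper values.

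**4. Which rates are plausible?** Protocol Section 1.5 expects no major overlap of toxicity between the two drugs, which points to the low end. Against very low rates, several DLT criteria (neutropenic fever, prolonged Grade 4 cytopenia, thrombocytopenia with bleeding) do not require attribution to leronlimab. Section 1.3.2 names marrow suppression as carboplatin's dose-limiting toxicity. Section 5.2 also counts leronlimab doses missed in Cycle 1 because of toxicity as DLTs.

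**5. Do the review steps settle it?** The four conditions in Section 3 and the DSMB trigger concern moving to the next dose level. The medical monitors' review in Section 8.5 controls the opening of Cohorts B and C. The DSMB's power to recommend stopping is discretionary. None of them bars three more patients at the same dose.

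**The case against.** The case for leaving this alone has several parts.

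- **No result changes.** The rule-derived MTD, the Phase II dose that follows from it and the maximum sample size are the same under both versions. This stands, and it limits the weight of the point.
- **The documents lean towards one rule.** The paragraph is the more specific text, it is the only version in the SAP, and the design is described as a standard 3+3. That shows what was probably intended. But the bullets are introduced as the way the scheme is carried out, and nothing readable ranks one text above the other.
- **Figure 3-2 may resolve it.** The graphic is not available in the text reviewed. Its note gives only the criterion of 0 or 1 DLT in six, which does not settle the matter. This remains an open limit on the check.
- **Review precedes the risky step.** A safety review follows the first three patients, and two or three listed DLTs would bring in the DSMB. Alert reviewers would probably step in. That lowers the risk, but it relies on discretion to override a written instruction.
- **The probabilities rest on chosen rates, and earlier experience is reassuring.** The first part is true. On the second, Section 1.4.3 reports no dose-limiting toxicity in earlier trials, but these were mostly in healthy or HIV-positive subjects, without carboplatin.
- **The DSMB might learn something from the extra patients.** The claim here covers only the mechanical rule; DSMB judgement was not modelled.

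**Conclusion.** The concern holds. The plan contains two dosing instructions that cannot both be followed when two or three of the first three patients have a DLT, and one of them exposes three more patients to a dose that has already failed the protocol's own rule. The probability is low: about 2% to 16% over assumed rates from 5/5/5% to 10/15/20%, higher if toxicity is worse, and lower to the extent that monitors or the DSMB intervene. It is avoidable patient exposure from an inconsistency of wording within an otherwise standard 3+3, and it does not threaten the trial's conclusions. It should be fixed because it concerns patient safety and the correction is simple. The conclusion that the extra patients cannot change the rule-derived MTD needs no assumption; the sizes rest on the assumed rates, and Figure 3-2 could not be checked.

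**What to change.** In the Phase Ib bullets of Protocol Section 3 and in the Synopsis copy, make the trigger for three more patients exactly one DLT among the first three. Add that two or three DLTs among the first three stop escalation, with the next lower dose taken as the MTD. This adopts the rule already in the following paragraph and in SAP Section 2.1. Confirm that the Figure 3-2 graphic agrees.

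The cost is a wording edit in two places in the protocol. The SAP text needs no change. No procedures or patients are added, and the rule-derived MTD and the maximum of 18 stay as they are.

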3.1 STUDY CENTER

Up to five centers in the United States (US).

3.2 STUDY POPULATION

The target population for this study is subjects with histologically confirmed mTNBC that express CCR5 (> 10% membranous staining completed at the laboratory at the Medical College of Wisconsin). Subjects should have measurable disease. Subjects must be naïve to chemotherapy in the metastatic setting (first-line) OR failed first-line combination of chemotherapy and a checkpoint inhibitor in the metastatic setting (excluding carboplatin).

This will be a multicenter trial. A total of up to 18 subjects in Phase Ib and 30 subjects in Phase II will be needed for this trial.

Eligibility will be evaluated by the study team according to the following criteria. Eligibility waivers are not permitted. Subjects must meet all of the inclusion and none of the exclusion criteria to be registered to the study.

3.3 ELIGIBILITY CRITERIA

3.3.1. Inclusion Criteria

Subjects are required to meet all of the following criteria for enrollment into the study:

1. Must have a histologically confirmed diagnosis of TNBC. Must demonstrate HER-2 negative (IHC 0, 1+, or fluorescence in situ hybridization (FISH) negative and ER< 1%, and PR < 1%, per ASCO/CAP criteria);
2. Demonstrate CCR5 + by IHC (>10% of primary or metastatic tumor cells shows membranous staining and/or high predominance of CCR5+ tumor-infiltrating leukocytes completed at the reference laboratory of [name] at Medical College of Wisconsin).

Note: This test will be done as part of the pre-screening period. It will be performed in archival metastatic tissue. If archival tissue is not available then, fresh biopsy will be done;

3. Be willing to provide tissue from a newly obtained core or excisional biopsy of a tumor lesion (in case archival tissue is not available);
4. Patients with stage IV de-novo disease or patients that develop recurrence after completion of neoadjuvant or adjuvant therapy are eligible;

Note: Patients who have been exposed to carboplatin in neoadjuvant or adjuvant setting will be allowed to enroll, if they have progressed \geq 6 months from completion of treatment.

5. Phase 1 study section:

Subjects must have disease recurrence and progression after \leq 2 line of therapy in metastatic setting but untreated with carboplatin

Phase 2 study section:

Subjects must be naïve to chemotherapy or untreated with carboplatin in metastatic setting (first-line) OR excluding carboplatin chemotherapy, subjects must have failed first-line combination of chemotherapy and a checkpoint inhibitor in metastatic setting;

6. Patients must have measurable disease based on RECIST v1.1;
7. Female patients, \geq 18 years of age;

8. Patients must exhibit a/an ECOG performance status of 0-1;
9. Life expectancy of at least 6 months;
10. Patients must have adequate organ and bone marrow function within 28 days prior to registration, as defined below:
 - leukocytes \geq 3,000/mcL;
 - absolute neutrophil count \geq 1,500/mcL;
 - platelets \geq 100,000/mcL;
 - total bilirubin: within normal institutional limits;
 - AST(SGOT) & ALT(SPGT) \leq 2.5 X institutional upper limit of normal (ULN) (applicable to all patients, irrespective of liver disease or metastasis); and
 - creatinine: within normal institutional limits.
11. Clinically normal resting 12-lead ECG at Screening Visit or, if abnormal, considered not clinically significant by the Principal Investigator.
12. Females of child-bearing potential (FOCBP) and males must agree to use two medically accepted methods of contraception with hormonal or barrier method of birth control, or abstinence, prior to study entry, for the duration of study participation and for 60 days after the last dose of study drug (Refer to Appendix 1). Should a female patient become pregnant or suspect she is pregnant while participating in this study, she should inform her treating physician immediately. NOTE: A FOCBP is any woman (regardless of sexual orientation, having undergone a tubal ligation, or remaining celibate by choice) who meets the following criteria:
 - Has not undergone a hysterectomy or bilateral oophorectomy; and
 - Has had menses at any time in the preceding 12 consecutive months (and therefore has not been naturally postmenopausal for $>$ 12 months).
13. FOCBP must have a negative serum pregnancy test at Screening Visit and negative urine pregnancy test prior to receiving the first dose of study drug; and
14. Patients must have the ability to understand and the willingness to sign a written informed consent prior to registration on study.

